COVER PAGE:

I am submitting a manuscript for consideration of registration in Clinical Trials. The manuscript is entitled “**Does timing of completion radical cholecystectomy determine the survival outcome in incidental carcinoma gallbladder – a single center retrospective analysis**”.

NCT number – not available

Date – 05.11.2021 (Results were last updated on 01.01.2019)

STUDY PLAN:

Surgical Gastroenterology department at our institute is a tertiary referral center for hepatobiliary malignancies; covers a large part of North and North-east India. The details and progress report of patients of Gallbladder Cancer (GBC) being referred to and treated at the institute is maintained in a prospective manner on hospital data base. This included demographic data, presenting complains, details of relevant investigations done outside and in the hospital, previous surgery, pre-hospital course, operative findings, post operative course and final histopathology. During the study period (Jan 2009 to Dec 2018), 1049 participants with the diagnosis of GBC (including 91 IGBC patients) were admitted; 239/958 participants with the diagnosis of GBC and 48/91 participants with the diagnosis of IGBC could undergo resection with curative intent. Information regarding adjuvant therapy, recurrence, and survival were retrieved through data maintained on follow up out-patient cards till December 2019. Few participants who stopped visiting the hospital were contacted telephonically or through letters.

Tumors were staged as per 8th edition of AJCC-TNM staging. Preoperative workup included contrast enhanced axial imaging (CECT – contrast enhanced computed tomography). In few cases with high risk features (residual disease on CT scan or late presentation), Positron Emission Tomography (PET) scan was added. Participants found fit for surgery and those with resectable disease on imaging were considered for the definite procedure. Laparoscopy was done preferably in those presenting beyond 4 weeks of index surgery or residual disease (local or nodal) on imaging to rule out metastasis. In absence of obvious distant metastasis (ascites, peritoneal nodules, mesenteric nodules, serosal nodules), inter-aortocaval (IAC) tissue was sent for evaluation of nodal metastasis. Once IAC node was found negative for deposits on frozen-section examination, radical re-resection was attempted. It included wedge resection of liver or Segment 4b/5 excision with regional lymphadenectomy. Extrahepatic bile duct excision was added in presence of positive cystic duct margin or direct invasion into the duct.

All available histopathology blocks and slides following the index cholecystectomy were re-reviewed by the pathologists at our institute. Tumor type, differentiation and primary T stage were documented for majority of cases. Interval between index cholecystectomy and date of re-operation was calculated for all the participants and divided into 3 groups: Early (<4weeks),

Intermediate (4-12 weeks) and Late (>12 weeks). Primary objective was to assess the effect of tumor characteristics and the time gap (between index surgery and re-resection) on overall survival following curative (R0/R1) resection.

Statistical Analysis:

Continuous variables were presented in median (range) while categorical data was expressed in frequency (%). A variable was considered as normally distributed when the Z-score was within ± 3.29 ($n \geq 50$). To compare the means/medians between two groups, independent samples t-test/Mann Whitney U test was used. To test the association between categorical variables, Chi square tests or Fisher exact test was used. Event free survival was calculated for the patients using the Kaplan-Meier survival plots using Log rank test and Breslow test. Univariate and multivariate Cox regression analysis were used to identify the predictors of survival. Variables found significant in Univariate analysis were included for multivariate analysis. A two tailed p-value of < 0.05 was considered statistically significant. Statistical package for social sciences version-23 (SPSS-23, IBM, Chicago, USA) and MedCals software was used for data analysis.

RESULTS:

During the study period, 48 participants {11 (22.9%) in Group 'E', 31 (64.5%) in Group 'I' and 6 (12.5%) in Group 'L'} underwent re-resection with curative intent. The demographic profile (age and gender), co-morbidities, tumor characteristics, extent of resection, resection margin and nodal clearance were similar in the three groups (each $p > 0.05$). Median age of participants with IGBC was 55 years and 2.7 times more common among females.

Similarly, presence of residual disease, grades of the tumor, primary stage of the tumor following index cholecystectomy, final stage after curative resection, adjuvant therapy and associated morbidity were statistically equal among the groups (each $p > 0.05$). No post operative mortality was recorded. The most common complication in the postoperative period was surgical site infection (SSI), recorded in 8 patients. Three patients required postoperative percutaneous drainage for intra-abdominal collection. No patient required prolonged hospital stay or reoperation.

Overall Survival (OS) and Disease-free survival (DFS):

Mean and median follow-up was 51.6 and 40.6 months, respectively (range: 1.2-130.6). Total 9(18.7%) patients were reported lost to follow up during the study period. Mean overall survival (OS) in study patients was 91.75(95% CI: 8.32-75.44) months. As OS percentage did not reach <50%, resultant median survival could not be computed. Similarly the mean DFS following curative resection was 85.63 (95% CI: 69.48-101.79) months (As the patient recurrence free survival percentage did not reach below 50%, resultant median recurrence free survival time could not be computed).

In present study, 29(60.4%) of those undergoing definitive surgery received chemotherapy. Around 58% received >1 cycle and 44% could complete their therapy. Radiotherapy was given to 42% participants. The most important indications for adjuvant therapy included good performance status with advanced stage and margin positive and/or node positive disease. OS among participants who received adjuvant therapy was similar to those who were not offered chemotherapy [88.10 (95% CI: 67.18-109.03) Vs 87.56 (95% CI: 61.66-113.45) months (p=0.916) (Fig 1). Similarly DFS among participants who received adjuvant therapy was similar to those who did not receive any post operative treatment. [86.18 (95% CI: 65.73-106.64) Vs 85.37 (95% CI: 59.82-110.91) months (p=0.915).

[figure not shown]

Figure 1: Overall impact of adjuvant therapy on event free survival.

[figure not shown]

Figure 2 : Overall event free survival in study patients as per timing of treatment.

Kaplan Meier method (log rank test) was used to compare the event free and disease-free survival time of the patients among the three groups. Though the participants operated within 4 weeks and between 4-12 weeks fared a better OS and DFS than those operated beyond 12 weeks, the difference could not achieve statistical significance. (Event free survival time (p=0.575) and

disease-free survival time (p=0.581))(Figures 2&3)

[figure not shown]

Figure 3: Overall disease free survival in study patients as per timing of treatment.

Survival Analysis:

On Univariate analysis of factors associated with significantly poor survival following curative resection were: presence of nodal metastasis, poor differentiation and lesions necessitating CBD excision. Other factors portending an unfavorable outcome included presence of residual disease, lympho-vascular invasion and delay in re-resection beyond 12 weeks, though the difference was not statistically significant. Primary tumor stage, resection margin and use of adjuvant therapy did not affect the overall survival (each $p > 0.05$). Residual disease was present in 20 out of 48 (41.6%) participants. The distribution of residual disease following re-resection, according to the index T-stage was (16% in T1, 29% in T2 and 72% in T3 tumors).

To further assess the predictors of survival among the participants, multivariate Cox regression analysis was used. Three variables (Node status, Grades and Extent of resection) which were significant on Univariate analysis were included in multivariate analysis. Results showed that disease grade was the only significant independent predictor of survival. Presence of positive

nodes ($p=0.052$) and the need for CBD excision (0.133) was associated with increased relative risk of disease related mortality, although the difference was not statistically significant.

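### The title question on timing is reported only as three-group log-rank p-values, with no hazard ratio or confidence interval behind the statements that late re-resection fares worse

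*Combined protocol and SAP*

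**What the plan says.** The title asks whether the timing of the completion operation determines survival. The Study Plan makes this part of the main aim: "Primary objective was to assess the effect of tumor characteristics and the time gap (between index surgery and re-resection) on overall survival". On the exposure it says: "Interval between index cholecystectomy and date of re-operation was calculated for all the participants and divided into 3 groups". Early is under 4 weeks; the others are "Intermediate (4-12 weeks) and Late (>12 weeks". No reason is given for these cut-points. The Results give the sizes: "48 participants {11 (22.9%) in Group 'E', 31 (64.5%) in Group 'I' and 6 (12.5%) in Group 'L".

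The Statistical Analysis section says "Event free survival was calculated for the patients using the Kaplan-Meier survival plots using Log rank test and Breslow test". It also describes univariate and multivariate Cox regression, the latter limited to variables significant on univariate analysis. How timing was coded in the Cox models is not stated.

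The section on overall and disease-free survival reports: "Kaplan Meier method (log rank test) was used to compare the event free and disease-free survival time of the patients among the three groups". The p-values are 0.575 (event-free) and 0.581 (disease-free). It says that patients in the two earlier groups "fared a better OS and DFS than those operated beyond 12 weeks", while noting non-significance. The Survival Analysis section includes, among factors said to point to a worse outcome, "delay in re-resection beyond 12 weeks, though the difference was not statistically significant". Timing is not among the three variables that entered the multivariate model (node status, grade, extent of resection).

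**The concern.** The exact interval exists for every patient, but the reported comparison uses only group membership. With 31 of 48 patients in one group, all variation between 4 and 12 weeks is set aside, and the group that carries the message has 6 patients. The text mentions neither a trend test nor a model with the interval as a continuous term.

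The larger gap is in the reporting. A bare p-value cannot separate no effect from too little information, and the text gives no estimate with which to judge the two directional sentences. The adjuvant-therapy comparison in the same section does give mean survival with 95% intervals for each group; the title question does not. One reader could take 0.575 to mean that timing is unimportant, and another could take the directional sentences to mean that delay is harmful.

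**Working it through.** **Inputs from the documents.** Group sizes 11/31/6 of 48; p = 0.575 and 0.581; two-sided 5% level; overall survival never fell below 50%.

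**Assumed.** The number of deaths, D, is not stated. Each death lowers a Kaplan-Meier curve by at least 1/48, so a curve that stays at or above 50% allows at most 24 deaths. The lower end of 10 is an assumption.

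**Group shares.** 11/48 = 22.9%, 31/48 = 64.58% (printed as 64.5%), 6/48 = 12.5%. These agree with the text apart from rounding. The log-rank p-values cannot be rebuilt without event data.

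**What the p-value allows.** If 0.575 comes from a 2-df test, chi-square = -2 ln(0.575) = 1.107. A 1-df contrast of the same groups cannot exceed this, whether it is a trend or Late against the rest. Its p-value is therefore at least 0.293. For disease-free survival, -2 ln(0.581) = 1.086 and p is at least 0.297.

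**Precision for Late (6) against the rest (42).** SE of the log hazard ratio ≈ 1/√(D × 0.125 × 0.875); the 95% interval is the hazard ratio divided and multiplied by exp(1.96 × SE).

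| Deaths | Expected Late deaths if no effect | SE | Factor either side |
|---|---|---|---|
| 10 | 1.25 | 0.96 | 6.5 |
| 14 | 1.75 | 0.81 | 4.9 |
| 24 | 3.0 | 0.62 | 3.4 |

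With 14 deaths, an observed hazard ratio of 1 would be compatible with about 0.2 to 4.9. Deaths needed for 80% power are (1.96 + 0.842)² / (0.125 × 0.875 × (ln HR)²): 150 for a hazard ratio of 2 and 60 for a hazard ratio of 3. Both exceed the ceiling of 24.

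**Does grouping lose power?** Simulated score tests, 48 patients, about 14 to 15 deaths. Two interval distributions were assumed: a lognormal matched to 22.9% below 4 weeks and 12.5% above 12 weeks (median 6.15 weeks, log SD 0.58), and a uniform distribution within each group (Late up to 26 weeks). Censoring is also assumed. Ranges cover the runs; the rows for 1.5 and 1.25 per doubling use the lognormal only.

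| True effect of delay | Three-group log-rank | Trend | Continuous log(weeks) |
|---|---|---|---|
| HR 2 per doubling, lognormal | 38–41% | 44–45% | 55–57% |
| HR 2 per doubling, uniform | 48% | 57% | 66% |
| HR 1.5 per doubling | 20% | 21% | 25% |
| HR 1.25 per doubling | 11% | 10% | 11% |
| Step beyond 12 weeks, HR 3 | 38–39% | 24% | 15–20% |
| U-shape, HR 3 (Early and Late v Intermediate) | 51–53% | 13–15% | 11–15% |

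With no effect, all three tests reject in 5–6% of runs.

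HR 2 per doubling is a large effect. Taking typical Early and Late intervals of about 2.9 and 16 weeks under the lognormal, it implies a Late-to-Early hazard ratio of 16/2.9 ≈ 5.5. HR 1.5 per doubling implies 1.5^log2(5.5) ≈ 2.7, and there the choice of test matters little.

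**The case against.** The strongest reply is that the three-group test is a reasonable choice. The primary objective states no direction or shape for the effect of the time gap. The 4-week cut also has a working role in the Study Plan, where laparoscopy was preferred for patients presenting later than that. The pattern the text describes, Early and Intermediate together doing better than Late, is a threshold, and for a threshold the three-group test has more power than a trend or log-linear term. This stands.

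A reader might therefore infer too much in two ways. One inference is that the least sensitive available test was used. The table shows that the ranking depends on the shape of the effect, which is unknown. The other is that a trend test would have rescued the result. If 0.575 is a 2-df p-value, no ordering of these groups could give a value below about 0.29. Only interval information within the groups could change the picture, and the documents do not show it. That the test ignored ordering is itself an inference from a single three-group p-value and the absence of any mention of trend.

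The authors can also say that both directional sentences admit non-significance, that univariate Cox regression was run and appears to have included delay beyond 12 weeks, and that Figures 2 and 3 (not available here) show the curves by timing group. All true. None of it puts a hazard ratio, an interval or a death count for timing into the available text, and admitting non-significance does not tell the reader how wide the uncertainty is.

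**Conclusion.** The point holds as one of estimation and reporting. The primary timing question has no effect size in the available text, and the directional sentences have no estimate behind them. Under the assumed 10 to 24 deaths, the interval for Late against the rest extends a factor of about 6.5 to 3.4 either side of the hazard ratio, with only 1 to 3 Late deaths expected if timing has no effect. The data therefore establish neither absence of effect nor harm from delay.

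The power loss from grouping is conditional. It is roughly 40% against 55% for a steep graded effect under the lognormal assumption with 14 to 15 deaths, small at a hazard ratio of 1.5 per doubling or less, and reversed for a step or a U-shape. The main limits are few deaths and 6 Late patients. No re-analysis removes them, so the gain from the change is an honest estimate with its uncertainty, and a significant result should not be expected.

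A related matter is the endpoint label. The objective names overall survival, the directional sentence speaks of overall survival, but the p-value is labelled event-free survival.

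**What to change.** 1. Keep the Early/Intermediate/Late Kaplan-Meier curves and the three-group log-rank test. Do not replace that test with a trend test.
2. Add a Cox model for overall survival with log(weeks from index cholecystectomy to re-resection) as a continuous term. Report the hazard ratio per doubling with its 95% confidence interval and a check for non-linearity.
3. Report the hazard ratio for Late against earlier re-resection with its 95% interval, plus deaths and numbers at risk in each group. With so few Late deaths, a profile-likelihood interval is preferable to the usual normal approximation.
4. Reword the directional sentences in the overall/disease-free survival section and in Survival Analysis to say that the effect of timing is inconclusive within the reported intervals.
5. State whether the p-value of 0.575 refers to overall survival, and use one endpoint name throughout.

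The cost is a re-run on data already held and a few changed sentences. The downside is that the continuous term assumes a log-linear shape and can miss a threshold, so the group hazard ratios should stand beside it. With this few deaths the non-linearity check will itself be weak.

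### The rule admitting only univariately significant variables leaves the re-resection time gap, the title exposure, without an adjusted survival estimate

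*Combined protocol and SAP*

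**What the plan says.** The cover page title asks: "Does timing of completion radical cholecystectomy determine the survival outcome in incidental carcinoma gallbladder". The Study Plan gives the primary objective as assessing the "effect of tumor characteristics and the time gap (between index surgery and re-resection) on overall survival following curative (R0/R1) resection", and defines three timing groups: under 4 weeks, 4-12 weeks and over 12 weeks.

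The Statistical Analysis section builds the multivariable Cox model by one rule: "Variables found significant in Univariate analysis were included for multivariate analysis". Significance is two-sided at 0.05. No variable is exempt.

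The results show how the rule worked:

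- **Group sizes (Results).** 11 early, 31 intermediate and 6 late patients, 48 in all. Baseline and tumor features are reported as not differing (each p>0.05). Grade, stage, adjuvant therapy and "associated morbidity were statistically equal among the groups".
- **Timing, unadjusted (OS and DFS section).** "participants operated within 4 weeks and between 4-12 weeks fared a better OS and DFS than those operated beyond 12 weeks", without statistical significance: "Event free survival time (p=0.575") and p=0.581 for disease-free survival. The first p-value carries the event-free label, in a passage that discusses OS and DFS.
- **Univariate Cox (Survival Analysis).** Delay beyond 12 weeks is listed as unfavorable but not significant. No reference group is given.
- **Multivariable Cox (Survival Analysis).** Node status, grade and extent of resection were entered. Only grade remained significant. Timing is absent.

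**The concern.** A significance screen can serve a search for predictors. It is a poor gate for the exposure that the study was set up to examine, because a low-powered p-value then decides whether the main question gets an adjusted answer. Here the gate closed. Timing is answered only by an unadjusted log-rank comparison and an unadjusted univariate statement.

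The reader therefore has no timing estimate that accounts for grade, the one factor reported as an independent predictor. Nor does the text give a hazard ratio and interval that would separate little effect from too few data.

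**Working it through.** The documents state no power, event target or target hazard ratio (HR), so there is no design figure to reproduce. The log-rank and Cox results cannot be rebuilt without patient data. The group counts do sum to 48 (11 + 31 + 6), with a late share of 6/48 = 0.125.

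**1. Number of deaths (not stated).**
- *Ceiling.* The OS section says: "As OS percentage did not reach <50%, resultant median survival could not be computed". With D deaths among 48 patients, censoring can only push the Kaplan-Meier curve lower, so its final value is at most (48 − D)/48. Keeping it at or above 0.5 requires D ≤ 24. The ceiling is reached only if nobody is censored before the last death. Since 9 patients were lost and follow-up starts at 1.2 months, 24 is a bound and not a likely value.
- *Working value.* Assume a constant hazard λ and that the printed mean OS of 91.75 months, restricted to the longest follow-up of 130.6 months, is right. Then (1 − exp(−130.6λ))/λ = 91.75 gives λ = 0.00577 per month. With mean follow-up of 51.6 months, D = 0.00577 × 48 × 51.6 = 14.3, about 14. The interval printed beside 91.75 excludes it, but 91.75 − 1.96 × 8.32 = 75.44, which fits a standard error and a lower limit printed as the two limits. The figure is rough: the fitted curve ends at exp(−130.6 × 0.00577) = 0.47, slightly below the 50% that the text says was not crossed.
- *Lower value.* 10 deaths, assumed.

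**2. Chance that a real timing effect fails the screen.** The contrast is late (6) versus the rest (42). This is an assumption, since the text names no reference group. The true HR of 2 is also assumed.

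Event formula: power = Φ(ln HR × √(D × 0.125 × 0.875) − 1.96).

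| Deaths | √(D × 0.109375) | × ln 2 | Power | Fails screen |
|---|---|---|---|---|
| 24 (ceiling) | 1.620 | 1.123 | 0.20 | 80% |
| 14 | 1.237 | 0.858 | 0.14 | 86% |
| 10 | 1.046 | 0.725 | 0.11 | 89% |

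A simulation at a mean of 14 deaths (20,000 datasets, univariate Cox Wald test, exponential survival, censoring assumed uniform on 1.2-130.6 months) rejects in 20.6%, so timing is dropped in about 79%. The formula is harsher because it puts 12.5% of deaths in the late group. At HR 2 the simulation puts 2.67 of 14 (19%) there.

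**3. Precision of a timing estimate.** SE(ln HR) = 1/√(D × 0.125 × 0.875), and the 95% interval is the HR times or divided by exp(1.96 × SE).
- 14 deaths: SE 0.808, factor 4.9.
- 10 deaths: SE 1/1.046 = 0.956, factor 6.5.
- 24-death ceiling: SE 0.617, factor 3.4, the best that this formula allows.

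A single pair of groups is less precise. For late versus early at 14 deaths in all, with deaths in proportion to patients: 14 × 17/48 = 4.96 deaths, SE = 1/√(4.96 × 6/17 × 11/17) = 0.94, factor exp(1.96 × 0.94) = 6.3.

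**4. What the balance tests can show.** Take a feature present in 40% of the 42 and, by assumption, 70% of the 6. Pooled proportion: (6 × 0.7 + 42 × 0.4)/48 = 0.4375. Null SE: √(0.4375 × 0.5625 × (1/6 + 1/42)) = 0.2165. Alternative SE: √(0.7 × 0.3/6 + 0.4 × 0.6/42) = 0.2018. Power = Φ((0.3 − 1.96 × 0.2165)/0.2018) = Φ(−0.62) = 0.27. A difference of 30 percentage points would usually give p>0.05.

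**The case against.** The strongest reply has four parts.

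- **The groups were reported as similar, including on grade and stage.** No imbalance is shown, and that stands. But p>0.05 in groups of 11, 31 and 6 does not show balance, and a balance test gives no adjusted estimate.
- **The study does not overclaim.** A reader might infer that it concludes timing has no effect. It does not: it says that late patients fared worse without reaching significance. A reader might also infer that the unadjusted result is confounded, or that adjustment would change it. Nothing in the documents shows either.
- **There are too few deaths to model more.** This largely stands, and the late group of 6 is the main limit. It argues for a small model and a plainly reported interval. It does not argue for leaving out the exposure while three other variables are entered.
- **The screen calculation assumes a contrast that the text does not specify.** This stands. The univariate analysis may have compared late with early patients or used a three-level factor, so the failure rates are illustrative. The structural point does not depend on them.

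**Conclusion.** The point holds. The entry rule makes no exception for the time gap, timing failed the screen, and the multivariable model omitted it. The text therefore gives no adjusted answer to the title question. Only part of the primary objective is affected: the tumor characteristics half is represented in the model by grade and node status.

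For an assumed HR of 2 and an assumed late-versus-rest contrast, timing would be dropped in roughly 79% to 89% of datasets over 10 to 24 deaths. Those limits mix methods: 79% is the simulation at 14 deaths and 89% the formula at 10. Failing the screen is thus weak evidence against an effect. The death count is the main unknown: 24 is a ceiling, 14 rests on a constant hazard and the printed mean, and 10 is arbitrary.

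This should be fixed. The omission itself is certain from the text; its size is approximate. Whether adjustment would alter the finding cannot be judged from the documents.

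**What to change.** Exempt the time gap from the univariate screen and keep it in the OS Cox model whatever its p-value.

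- **Main adjusted model.** The three timing groups defined in the Study Plan, with the reference group stated, plus grade as one term. Use a penalised (Firth) fit, because late deaths are sparse: in the simulation at 14 deaths, about 1.7 (HR 1) to 2.7 (HR 2) fall among the 6 late patients.
- **Sensitivity analyses, labelled post hoc.** Late versus the rest, time as a continuous term, and a model adding node status. Node status may lie on the path from delay to death, so it should not be in the main model by default.
- **Reporting.** Unadjusted and adjusted timing HRs with 95% confidence intervals, deaths in each timing group, and the number missing grade. That last count is needed because the Study Plan says only: "Tumor type, differentiation and primary T stage were documented for majority of cases". Label the whole rerun post hoc and exploratory, and call a wide interval inconclusive.

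The cost is a rerun on existing data, a record check for grade, possibly other software for the penalised fit, and changed wording. Two timing terms and one grade term leave 14/3 = 4.7 deaths per term (10/3 = 3.3 at 10 deaths, 24/3 = 8 at the ceiling). The result will probably be inconclusive, since re-modelling leaves the late group at 6.

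### Residual disease and final stage, found after the delay has elapsed, are reported as group similarities and not as outcomes, and no timing estimate is adjusted for factors fixed at the index operation

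*Combined protocol and SAP*

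**What the plan says.** The Study Plan defines the exposure: "Interval between index cholecystectomy and date of re-operation was calculated for all the participants and divided into 3 groups", with cut-points at 4 and 12 weeks. It also gives the aim: "Primary objective was to assess the effect of tumor characteristics and the time gap (between index surgery and re-resection) on overall survival".

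The Results report that "48 participants {11 (22.9%) in Group 'E', 31 (64.5%) in Group 'I' and 6 (12.5%) in Group 'L'} underwent re-resection". They then make two similarity statements, each resting on p > 0.05. The first covers demographics, co-morbidities, tumor characteristics, extent of resection, margin and nodal clearance. The second covers "presence of residual disease, grades of the tumor, primary stage of the tumor following index cholecystectomy, final stage after curative resection", and ends by saying that these together with "adjuvant therapy and associated morbidity were statistically equal among the groups".

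The Statistical Analysis section has one rule for multivariable Cox regression: variables significant on univariate analysis go in. The Survival Analysis section applies it: "Three variables (Node status, Grades and Extent of resection) which were significant on Univariate analysis were included in multivariate analysis". Delay beyond 12 weeks was not significant on univariate analysis and did not enter. The other timing results are log-rank comparisons of the three groups (p = 0.575 and p = 0.581).

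**The concern.** A factor that is fixed when the interval starts can confound the effect of delay. A factor observed when the interval ends can be a result of delay. The two need opposite handling: adjust for the first, and report the second as an outcome. The plan does not separate them.

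Two things follow. First, similar residual disease and final stage across the timing groups do not show that the groups were comparable to begin with. They are a partial answer to the study question, and one given without rates by group, effect sizes or confidence intervals. Second, the plan offers no timing estimate of the kind the objective needs. The results it reports are unadjusted, so they may be confounded by index stage or grade. Had timing been significant, the entry rule would have adjusted it for node status and extent of resection, leaving only whatever part of the effect does not act through them.

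**Working it through.** **1. When each variable is known, and how it is used.** Timing of knowledge is read from the Study Plan; use is read from Results and Survival Analysis.

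| Variable | Known at | Named in group comparison | Multivariable Cox |
|---|---|---|---|
| Primary T stage | index specimen | yes | no (univariate only) |
| Grade | index specimen (assumed to be the re-reviewed differentiation) | yes | yes |
| Residual disease | re-resection | yes | no (univariate only) |
| Final stage | after re-resection | yes | no (in no reported Cox analysis) |
| Node status | re-resection (lymphadenectomy) | not by name | yes |
| Extent of resection | re-resection | yes | yes |
| Margin | re-resection | yes | no (univariate only) |
| Time gap | the exposure | defines the groups | no (univariate only) |

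Four variables known only at or after re-resection (residual disease, final stage, extent of resection, margin) are therefore named in the similarity statements. Two (node status, extent of resection) are in the multivariable model. Timing is not in that model, so the model contains no delay estimate that could have been attenuated.

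**2. The plan's counts.** 11 + 31 + 6 = 48, and 20/48 = 41.67% with residual disease (stated as 41.6%). The documents give no residual-disease rate by timing group and no number of deaths.

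**3. What node adjustment would do if timing were in the model.** All inputs here are assumed. Let pS and pL be the node-positive proportions after short and long delay, let H be the hazard ratio for positive nodes, and let delay act only through nodes. The hazard ratio for delay at time zero is (pL·H + 1 − pL)/(pS·H + 1 − pS).

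- pS = 0.20, pL = 0.40, H = 3: (1.2 + 0.6)/(0.6 + 0.8) = 1.29
- pS = 0.20, pL = 0.50, H = 4: (2.0 + 0.5)/(0.8 + 0.8) = 1.56
- pS = 0.25, pL = 0.60, H = 5: (3.0 + 0.4)/(1.25 + 0.75) = 1.70

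In each case the node-adjusted value is 1.0. A large simulated cohort (node-positive 30% if not late, 60% if late; node hazard ratio 3; grade hazard ratio 2; no direct effect of delay) agrees. The Cox hazard ratio for late surgery was 1.35 with timing alone, 1.35 with timing and grade, and 0.99 once node status was added.

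**4. What a p-value above 0.05 can show about residual disease.** Take Late (6) against the rest (42), Fisher's exact test, two-sided 0.05, with the overall rate held at 20/48. For an assumed late rate r, the rate in the rest is (20 − 6r)/42.

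- 60% against 39%: power 10%
- 70% against 38%: power 23%
- 80% against 36%: power 43%

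Even an observed 5/6 against 15/42, an odds ratio of (5/1)/(15/27) = 9, gives p = 0.069. The three-group chi-square test has power of about 17%, 36% and 60% for assumed Early/Intermediate/Late rates of 30/42/60%, 25/42/70% and 20/42/80%.

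**5. What the data can support.** The overall survival curve did not fall below 50%, and each death lowers a Kaplan-Meier curve by at least 1/48, so there were at most 24 deaths. For Late against the rest, the standard error of the log hazard ratio is about 1/√(24 × 6/48 × 42/48) = 1/√2.625 = 0.617. The 95% limits are then the estimate divided and multiplied by exp(1.96 × 0.617) = 3.35. Power with 24 deaths (Schoenfeld formula) is 20% for a hazard ratio of 2 and 43% for 3.

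**The case against.** The strongest reply is that nothing was over-adjusted. The reported model has no timing term, and the unadjusted timing results already include any effect that runs through nodes, residual disease or stage. This stands. A reader might infer that the null timing finding arose because node status absorbed the effect of delay; the documents do not support that. Nor do the hazard ratios in step 3 measure an error in any reported number.

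It is also fair that the second similarity sentence includes adjuvant therapy and morbidity, which are plainly post-operative. The list can therefore be read as description, and no sentence claims that the groups are unconfounded. Comparing residual disease across the groups is already a crude test of whether it varies with delay. But without rates or intervals, and with 6 late patients, that test says little (step 4).

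Third, the variables may not be pure mediators. Residual disease rises with index T stage (16%, 29%, 72%), so some may have been left at the index operation. Bile duct excision could follow a positive cystic duct margin, which may predate the interval. This also stands: a reader should not infer that delay caused the residual or nodal disease.

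Finally, the objective also covers tumor characteristics, and a prognostic model with nodes and grade serves that part. Agreed; the model needs a label, not removal.

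**Conclusion.** The point holds in a limited form and should be corrected. Residual disease and final stage follow the exposure interval, are presented as similarities next to factors fixed before it, and are not analysed as outcomes of delay. The plan provides no timing estimate adjusted for index T stage and grade. Its single entry rule would give the wrong kind of adjusted estimate for the stated objective, "Primary objective was to assess the effect of tumor characteristics and the time gap (between index surgery and re-resection) on overall survival", if timing had qualified.

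No reported figure is shown to be biased by adjustment. The size of the problem under the rule is known only for assumed inputs: a hazard ratio of 1.29 to 1.70 reduced to 1.0. The conclusion rests on two readings: that node status was determined at re-resection, and that the grade analysed is that of the index specimen. Nodal status as a group-similarity factor is only inferred, because the Results name nodal clearance and tumor characteristics rather than node status itself.

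**What to change.** 1. Take residual disease, final stage, nodal status and margin out of the similarity statements. Report each by interval as an outcome, with effect size and 95% confidence interval; for example, logistic regression of residual disease (20/48) on interval in weeks, adjusted for index T stage. With T stage as a linear score this is two parameters, or 20/2 = 10 cases per parameter.
2. Fit one small Cox model for overall survival with timing forced in, adjusted only for index T stage and grade. With one term each, that is at most 24/3 = 8 deaths per parameter, so nothing further should be added.
3. Keep the node, grade and extent-of-resection model, label it prognostic only, and draw no statement about timing from it.

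The cost is relabelling plus a few small models on existing records; no new patients are needed. Three limits should be stated with the results. Intervals will be wide (step 5). Index T stage and differentiation were documented only for most cases, so the number missing must be given. And only the 48 of 91 patients with incidental cancer who were resected are seen, so progression to unresectable disease during the delay among the other 43 stays outside any of these models.
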